- ^t A single 15 mL serum sample will be retained for evaluation in the event of an unexpected safety finding; retained samples may be destroyed after completion of the clinical study report.
- ^u Vital signs measurements and ECGs should be performed predose, unless otherwise specified. Vitals signs include body temperature, heart rate, respiratory rate, and systolic and diastolic blood pressure.
- ^v Copper- and molybdenum-controlled diet will be initiated after registration/inclusion. Participants will remain on a copper/molybdenum controlled diet throughout both the inpatient Period 1 (Day -8 to Day 9) and inpatient Period 2 (Day 23 to Day 40); during this time participants will be strongly encouraged to complete all meals. While not in the CRU, participants will be encouraged to adhere to their usual copper-controlled diet.
- ^w For each input/output balance period, 24-hour urine samples are to be collected for measurement of copper and molybdenum.
- ^x For fecal samples, each individual sample will be independently collected with record of date, time, and weight of the sample.
- Abbreviations: AE = adverse event; BMI = body mass index; C-I = check-in; Cu = copper; D = day; ECG = electrocardiogram; EOS/ET = End of Study or Early Termination; HIV = human immunodeficiency virus; HR = heart rate; LBC = labile bound copper; Mo = molybdenum; OP = outpatient; PD = pharmacodynamic; PK = pharmacokinetics; PUF = plasma ultrafiltrate; UNS = unscheduled; WD = Wilson disease.

Table 2: Schedule of Pharmacokinetic and Pharmacodynamic Assessments on Days 1, 25, 29, and 39

Time point (hours) ^a	-0.5	0	1	2	3	4	5	6	8	12	24
Blood sampling for PK: Plasma total Mo and PUF-Mo PD: Plasma total and PUF-Cu, LBC, ceruloplasmin, ceruloplasmin-bound Cu	X			X		X	X	X	X	X	X ^b

Note: Windows for PK/PD time points will be defined as $\pm 10\%$ of the nominal time point. On Days 1 and 39, triplicate 12-lead ECG will be collected at 4 hours postdose. When multiple procedures are scheduled to occur at the same time, the following order of events should be strictly adhered to whenever possible: ECG, vital signs, blood sampling (eg, for PK/PD), study intervention administration, and meal.

^a Time points are relative to dosing (0 hours).

^b Hour 24 PK/PD sampling is to occur just prior to the next-day dose of ALXN1840.

Abbreviations: Cu = copper; LBC = labile bound copper; Mo = molybdenum; PD = pharmacodynamic; PK = pharmacokinetic; PUF = plasma ultrafiltrate.

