Following single-dose administration of 60 mg ALXN1840, total molybdenum peaked at approximately 4.54 hours with a terminal elimination half-life measured at approximately 51 hours. In Study WTX101-201, the PK of ALXN1840, based on total molybdenum, indicated that exposure in participants with WD at a dose of 30 mg appeared consistent with previous results from healthy participants. The half-life was estimated to be approximately 24 hours at steady state on Days 84 and 168 and was shorter than estimated in previous studies. Based on a total molybdenum PK half-life of approximately 24 - 51 hours, total molybdenum steady state may conservatively be reached within approximately 10 - 12 days. Nevertheless, results (as

measured by total molybdenum) obtained from the ALXN1840 balance study in the LEC WD rat model suggested that approximately 30% of a single dose of ALXN1840 remained in the liver by Day 7, indicating the possibility of tissue accumulation, particularly in the setting of high liver copper concentration ([Plitz, 2019](#)).

If the half-life of ALXN1840 in liver were longer than that of the systemic compartment, the accumulation may not be readily detected in the absence of a longer treatment period and with characterization of the terminal elimination period. An alternative approach to assessing steady state using total molybdenum PK is to assess whether the total molybdenum intake is equal to the total molybdenum output; this approach may detect any significant ongoing accumulation in the liver or other tissues.

Detailed descriptions of the chemistry, pharmacology, efficacy, and safety of ALXN1840 are provided in the Investigator's Brochure (IB).

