4. DESCRIPTION OF THE PROTOCOL

[figure not shown]
Study ALXN1840-WD-204 will be conducted as an open-label, repeat-dose study to evaluate the effects of ALXN1840 on copper balance in participants with Wilson Disease (WD).

Treatment-experienced (which includes standard of care therapies or ALXN1840) and treatment-naïve participants are eligible for this study. Eligible patients will be classified into one of two cohorts:

- Cohort 1 (treatment experienced): Patients who have received WD therapy for > 28 days
- Cohort 2 (treatment naïve): Patients who have received WD therapy for ≤ 28 days

Following Screening and enrollment, participants will check-in to the clinical research unit (CRU) on Day -8 for the Run-in Period. The purpose of the Run-in Period is to support diet equilibration (Day -7 through Day -5) and measure pretreatment copper and molybdenum balance (Day -4 through Day -1). Participants will remain on a copper/molybdenum-controlled diet throughout both the Inpatient Period 1 (Day -8 to Day 9) and Inpatient Period 2 (Day 23 to Day 40). The study design schematic is presented in Figure 1. While not in the CRU, participants will be encouraged to adhere to their usual copper-controlled diet.

Figure 1: Study Design Schematic

1. Participants eligible for the study will be enrolled on Day -7 and initiated on a copper- and molybdenum-controlled diet, which will be continued during Treatment Period 1 and Treatment Period 2 when in the CRU, through Day 39.
2. Participants will be admitted to the CRU for Treatment Period 1 on Day -8 and may be discharged on Day 9 or remain in the CRU for their own safety or to maintain the integrity of the conduct of the study. Participants who are discharged will be re-admitted on Day 22 or Day 23 for Treatment Period 2 and will remain in house until Day 40. To ensure flexibility, the Outpatient Period may be extended up to an additional 14 days with Investigator approval. In this situation, participants will be given additional study drug to support daily dosing throughout the Outpatient Period. In such cases, the actual Outpatient Period duration will be recorded and the participant will continue Inpatient Period 2 at Day 23.
3. Participants will be administered ALXN1840 at a dose of 15 mg/day on Day 1 through Day 28 and then increase to 30 mg/day on Day 29 through Day 39.
4. Participants will have 3 intake and output collection periods including:
 - Baseline Day -4 through Day -1

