5.1.2. Secondary Objectives and Endpoints

The secondary objectives and endpoints are given below. Molybdenum balance measurements are conducted in a similar manner to copper balance measurements (Section 5.1.1.1).

Objectives	Endpoints
Assess change in copper balance in response to ALXN1840 15 mg/day and 30 mg/day during ALXN1840 accumulation and at steady state periods versus the pretreatment Baseline in participants with WD	Change in mean daily copper balance as measured by the calculated difference between copper intake (in food and drink) and copper output (in feces and urine) from pretreatment Baseline (Days -4 through -1) and ALXN1840 accumulation and steady-state periods for each dose
Investigate the effect of ALXN1840 (15 mg/day and 30 mg/day) on the disposition of copper in participants with Wilson Disease (WD)	Copper quantified in food, drink, feces, and urine, including plasma total and labile bound copper (LBC) during ALXN1840 accumulation and steady-state periods for each dose
Investigate the effect of ALXN1840 on the disposition of molybdenum at steady state at 15 mg/day and 30 mg/day in participants with WD	Molybdenum quantified in food, drink, feces, and urine, plasma total molybdenum at ALXN1840 steady state
Assess steady-state total molybdenum balance as a measure of ALXN1840 15 mg/day and 30 mg/day in participants with WD	Mean daily molybdenum balance as demonstrated through measurement of molybdenum intake (in food, drink, and ALXN1840), and molybdenum output (feces and urine) representing ALXN1840 steady state
Assess accumulation of molybdenum with ALXN1840 treatment at 15 mg/day and 30 mg/day in participants with WD	Accumulation of molybdenum as determined by molybdenum balance
Determine the steady-state plasma pharmacokinetic (PK) of total molybdenum and plasma ultrafiltrate (PUF) molybdenum (as surrogate measures of ALXN1840, 15 mg and 30 mg) in participants with WD	PK parameters for plasma total and PUF molybdenum

Note: The accumulation period refers to time from initiation of ALXN1840 (Day 1) to expected steady state at Day 10, based on 5 times the half-life of 2 days.

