7.4.3. Pharmacokinetic Parameter Analyses

The following plasma PK parameters, as data permit, will be calculated for total molybdenum and PUF molybdenum (as surrogate measures of ALXN1840 PK) after dosing on Days 1, 25, 29 and 39 using noncompartmental methods with Phoenix® WinNonlin® (Certara USA Inc., Princeton, New Jersey) Version 8.0 or higher or SAS Version 9.4 or higher (SAS Institute Inc., Cary, North Carolina), as applicable. Calculations will be based on the individual actual sampling times relative to the actual ALXN1840 reference dosing times recorded during the study.

- Time delay between the time of dosing and time of appearance of molybdenum concentration (T_{lag}) in plasma
- Maximum observed concentration (C_{max})
- Dose-normalized C_{max} (C_{max_n}); n = dose normalized
- Time to maximum concentration (T_{max})
- Trough (pre-dose) concentration observed at the start of the dosing interval (C_{trough})
- Time of last quantifiable concentration (T_{last})
- Observed concentration at the end of the dosing interval (C_{τ} , where $\tau = 24$ h)
- Area under the plasma concentration versus time curve (AUC) from time 0 to the last quantifiable concentration (AUC_t)
- Dose-normalized AUC_{t_n} (AUC_{t_n}); n = dose normalized
- AUC from time 0 to infinity (AUC_{∞}) (Day 1 only)
- Dose-normalized AUC_{∞} (AUC_{∞_n}); n = dose normalized
- AUC over the dosing interval (AUC_{τ})
- Accumulation ratio (AR) calculated as C_{max} , C_{trough} , and AUC_{τ} after repeat dosing divided by those after initial dosing on Day 1:

For 15 mg/day:

- $C_{max,Day25}/C_{max,Day1}$
- $C_{trough,Day26}/C_{trough,Day2}$
- $AUC_{\tau,Day25}/AUC_{\tau,Day1}$

For 30 mg/day:

- $C_{max,Day39}/C_{max,Day29,adjusted}$
- $C_{trough,Day40}/C_{trough,Day30,adjusted}$
- $AUC_{\tau,Day39}/AUC_{\tau,Day29,adjusted}$

Note: total molybdenum and PUF molybdenum concentration-time profiles on Day 28 after the last 15 mg ALXN1840 dose will be extrapolated to Day 29 (0-24 hr) and subtracted from the

observed Day 29 concentration-time profiles after the first 30 mg ALXN1840 dose for the estimation of the $C_{\max, \text{Day}29, \text{adjusted}}$, $C_{\text{trough}, \text{Day}30, \text{adjusted}}$, and $AUC_{\tau, \text{Day}29, \text{adjusted}}$.

- Apparent terminal phase elimination rate constant (λ_z)
- Terminal elimination half-life ($t_{1/2}$)
- Apparent total body clearance (CL/F) of ALXN1840 from plasma
- Apparent volume of distribution (V_d/F)

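### T_lag on Days 25, 29 and 39 says nothing about absorption lag, because total molybdenum from earlier daily doses is already in plasma at dosing

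*SAP*

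**What the plan says.** SAP 7.4.3 opens its parameter list with "The following plasma PK parameters, as data permit, will be calculated for total molybdenum and PUF molybdenum" and fixes the days: "after dosing on Days 1, 25, 29 and 39 using noncompartmental methods". T_lag is the first entry, defined as the "Time delay between the time of dosing and time of appearance of molybdenum concentration". It carries no day limit, no correction for what is in plasma before the dose, and no algorithm.

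The same list does limit another parameter: AUC∞ is marked as Day 1 only. It also deals with carry-over once. The Day 28 profile "will be extrapolated to Day 29 (0-24 hr) and subtracted from the" observed Day 29 profile, but only to obtain the adjusted C_max, C_trough and AUC_tau for Day 29.

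The section then summarises PK parameters by analyte, dose and day. Its rule for values below quantification sets to zero only those that precede the first measurable concentration, so it does not act on a pre-dose sample that is measurable.

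Protocol 9.4.4 lists T_lag without naming days. The day assignment therefore comes from the SAP.

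**The concern.** T_lag is meaningful when the analyte is absent, or at a known background, at the time of dosing. On Days 25, 29 and 39 the participant has been dosed daily for weeks. If molybdenum is already present, the defined quantity cannot reflect the delay before the current dose is absorbed.

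PK parameters for total and PUF molybdenum are a secondary endpoint, and the SAP states that its outputs support regulatory submissions. With 4 days × 2 analytes there are eight T_lag summaries by day. Those for the later days would sit in the same table as Day 1 with nothing to tell the reader that they are not measurements of lag.

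**Working it through.** **Inputs**
- Dosing (SAP 4): "Participants will be administered ALXN1840 at a dose of 15 mg/day on Day 1 through Day 28 and then increase to 30 mg/day" from Day 29 to Day 39. Earlier doses on the planned schedule: 24 before Day 25, 28 before Day 29, and 28 + 10 = 38 before Day 39. An extended outpatient period would only add doses.
- Half-life (Protocol 2.2): "Based on a total molybdenum PK half-life of approximately 24 - 51 hours".
- Steady state (SAP 5.1.2): "expected steady state at Day 10, based on 5 times the half-life of 2 days".
- Sampling (Protocol 1.3, Table 2, row "Blood sampling for PK: Plasma total Mo and PUF-Mo"): marks at -0.5, 2, 4, 5, 6, 8, 12 and 24 h. The 1 h and 3 h columns are empty in the extracted table.

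**Step 1. The plan's own figure.** 5 × 2 days = 10 days, as stated. At the ends of the range, 5 × 24 h = 5.0 days and 5 × 51 h = 10.6 days. All three later profile days fall after this.

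**Step 2. Carry-over at dosing.** The fraction remaining after 24 h is 2^(-24/t½): 2^(-24/24) = 0.50 and 2^(-24/51) = 0.72. Summing over earlier doses, in units of the initial level from one 15 mg dose, the pre-dose level is R = Σ D_k × 2^(-24k/t½). Here k is the number of days since the dose, and D_k is 1 for 15 mg and 2 for 30 mg. As a share of that day's peak, with input treated as instantaneous, this is R / (R + D), where D is that day's dose.

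| Day | D | R, t½ 24 h | R, t½ 51 h | Share of peak, 24 h | Share of peak, 51 h |
|---|---|---|---|---|---|
| 25 | 1 | 1.000 | 2.592 | 0.500 | 0.722 |
| 29 | 2 | 1.000 | 2.593 | 0.333 | 0.565 |
| 39 | 2 | 1.999 | 5.086 | 0.500 | 0.718 |

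Predicted pre-dose total molybdenum is thus about 33 to 72% of the peak. Instantaneous input overstates the peak, so these shares err on the low side.

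**Step 3. How short the half-life would have to be.** For the steady-state trough to fall below 1% of peak, 2^(-24/t½) < 0.01, so t½ < 24 / log2(100) = 3.6 h. That is far below 24 h.

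**Step 4. What a first-measurable-concentration rule returns.** The rule takes the last sampling time before the first quantifiable value, and 0 if the pre-dose sample is quantifiable. For illustration I assumed a quantification limit of 1% of one 15 mg dose's initial level, an absorption rate of 0.6/h and no dietary background:
- Day 1: true lags of 0, 1, 2.5 and 4.5 h return 0, 0, 2 and 4 h.
- Days 25, 29 and 39: all four return 0, at both half-lives.
- Day 1 with an assumed background of 2%, above the limit: a true lag of 2.5 h returns 0.

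**Step 5. PUF molybdenum.** The 24 to 51 h range is for total molybdenum only. The SAP plans the Day 29 subtraction, and C_trough accumulation ratios, for both analytes, so it expects PUF carry-over too. That makes the same result likely; it does not show it.

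**The case against.** The best defence is that the SAP gives no T_lag algorithm and qualifies the whole list by what the data permit, so an analyst could leave T_lag blank on the later days. Part of this stands: zero follows only from a first-measurable-concentration rule, and the alternative is that T_lag is undefined. But a measurable pre-dose sample is not missing data and does not by itself trigger the qualifier. Either outcome calls for the same edit.

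It is also fair that individual concentrations are listed by participant, so a careful reader could see the pre-dose values. That does not repair the summary table.

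A third defence is that T_lag could be kept on later days as the time to the first rise above pre-dose. This is possible but biased late, because the carry-over is falling meanwhile. Over 2 h it drops by 1 − 2^(-2/24) = 5.6% or 1 − 2^(-2/51) = 2.7%, and the new dose must first make that up. Day 1 only is simpler, though not the only workable choice.

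The objection on consequence stands in full. The study is exploratory and descriptive, in about 10 participants. T_lag does not enter the accumulation ratios, the dose-proportionality model (dose-normalised C_max and AUC_t) or copper balance.

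**Conclusion.** The point holds and is of low severity. As written, SAP 7.4.3 yields a T_lag for total molybdenum on Days 25, 29 and 39 that is 0 or undefined whatever the true lag. Three of the eight summaries are affected on the documents' figures, and three more (PUF molybdenum) are likely to be. This rests on daily dosing as planned, the 24 to 51 h half-life, mono-exponential decline, and a quantification limit below the predicted troughs; the documents give no limit.

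A reader might infer three stronger things that the documents do not support:
- **That the SAP will report an absence of absorption lag.** It says no such thing; that would be a reader's interpretation of a tabulated zero.
- **That all six later summaries are certainly zero.** The documents give neither a T_lag algorithm nor a PUF half-life.
- **That the table will show a spurious change from Day 1.** Protocol 4.2 notes that measured molybdenum includes dietary molybdate, and SAP 7.1.3.2 summarises baseline total and PUF molybdenum. The Day 1 pre-dose sample may therefore be measurable too, and Day 1 would then also return 0.

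**What to change.** In SAP 7.4.3:
1. Mark T_lag as Day 1 only, as is done for AUC∞, and report it as not applicable on Days 25, 29 and 39.
2. On Day 1, derive it from pre-dose-corrected concentrations as the last nominal sampling time, with the pre-dose sample set to 0 h, before the first rise above the pre-dose value by a margin fixed in advance from the assay's validated precision. Setting pre-dose to 0 h prevents a result of -0.5 h. State the use of nominal times as an exception, since the section otherwise uses actual times.
3. Add a note on resolution. With the Table 2 samples as extracted (pre-dose, 2, 4, 5, 6, 8, 12 and 24 h), a lag shorter than 2 h is reported as 0, and longer lags are rounded down to the preceding sample. For scale, Protocol 2.2 gives a time to peak of about 4.54 h after a single 60 mg dose. Check Table 2 first for 1 h or 3 h marks lost in extraction.

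The cost is a few lines of SAP text and three uninformative table rows per analyte. No new samples are needed, and Protocol 9.4.4 can stay as it is because it names no days for T_lag.

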1.2. Schema

Figure 1: Study Schematic

- Participants eligible for the study will be enrolled on Day -7 and initiated on a copper- and molybdenum-controlled diet, which will be continued during Treatment Period 1 and Treatment Period 2 when in the CRU, through Day 39.
- Participants will be admitted to the CRU for Treatment Period 1 on Day -8 and may be discharged on Day 9 or remain in the CRU for their own safety or to maintain the integrity of the conduct of the study. Participants who are discharged will be re-admitted on Day 22 or Day 23 for Treatment Period 2 and will remain in house until Day 40. To ensure flexibility, the Outpatient Period may be extended up to an additional 14 days with Investigator approval. In this situation, participants will be given additional investigational product to support daily dosing throughout the Outpatient Period. In such cases, the actual Outpatient Period duration will be recorded and the participant will continue Inpatient Period 2 at Day 23.
- Participants will be administered ALXN1840 at a dose of 15 mg/day on Day 1 through Day 28 and then increase to 30 mg/day on Day 29 through Day 39. During the Outpatient Period, participants will use SMS text messaging to confirm study intervention administration.
- Participants will have 3 intake and output collection periods including:
 - Baseline Day -4 through Day -1
 - Day 1 through Day 8 (I/O for 15 mg)
 - Day 25 through Day 39 (Days 25 through 28, I/O for 15 mg; Days 29 through 39, I/O for 30 mg)
- During these periods all intake (including food and drink) and output (including urine and feces) will be collected and assessed for copper and molybdenum.
- Blood sampling for PK/PD will be as follows:
 - PK/PD collection (24-hour): Days 1, 25, 29, and 39
 - Pre-dose PK/PD sampling days: Days 4 - 7, Days 26 - 28, Days 30 - 38
 - End of Study Visit Day 54 +/- 2 days

Abbreviations: AP = accumulation period; CRU = clinical research unit; EOS = End of Study; I/O = input/output; PD = pharmacodynamic; PK = pharmacokinetic; SS = steady state.

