- ^k A full physical examination will be performed at Screening, at check-in for the study, and at the End of the study/Early Termination Visit. A physical examination should also be performed on any participants with ongoing adverse events prior to discharge from the unit. Otherwise, a symptom-driven physical examination may be performed at other times, at the Principal Investigator's discretion.
- ^l Height at screening only.
- ^m While in the CRU, study intervention will be administered after an overnight fast (ie, at least 10 hours) at the same time every morning; drug is to be administered with 240 mL of water and meals should be delayed a minimum of 2 hours after dosing. As an outpatient, participants are expected to take ALXN1840 at approximately the same time daily (+/-1 hour). Participants should take the medication with a glass of water on an empty stomach; meals should be delayed a minimum of 2 hours after dosing.
- ⁿ During the outpatient period, participants will use SMS text messaging to confirm study intervention administration.
- ^o Blood sampling for PK/PD will occur before ALXN1840 administration and represents a predose trough. See [Table 2](#) for PK/PD sampling on Days 1, 25, 29, and 39.
- ^p PK/PD collection will include timepoints described in the schedule of PK/PD assessment for Days 1, 25, 29, and 39 ([Table 2](#)).
- ^q Samples for serum chemistry will be obtained following a fast of at least 8 hours at the Screening Visit and at check-in. In case of rechecks, and postdose serum chemistry, participants may not have fasted for 6 or 8 hours before the serum chemistry sample is taken.
- ^r Laboratory assessment including chemistry, hematology, and coagulation parameters should be performed on Days -8, -1, 8, 23, and 28 only.
- ^s Menstruation check is for women only; women of childbearing potential should only be enrolled after a negative serum pregnancy test result at Screening. Additional urine pregnancy testing will be standard for the protocol unless serum testing is required by site policies, local regulation, or Institutional Review Boards (IRBs)/Independent Ethics Committees (IECs) (Section 10.2). In addition to pregnancy tests detailed at the visits in the SoA, females of childbearing potential will be required to perform urine pregnancy tests at least every 4 weeks at their home or the study site throughout their time in the study.

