9.4.4. Pharmacokinetic, Pharmacodynamic, and Biomarker Analyses

For PK, PD, and biomarker endpoints, analyses will be performed using the PK/PD Analysis Set. The following plasma PK parameters will be calculated for total molybdenum and PUF molybdenum (as surrogate measures of ALXN1840 PK) using noncompartmental methods with Phoenix® WinNonlin® (Certara USA Inc., Princeton, New Jersey) Version 8.0 or higher or SAS Version 9.3 or higher (SAS Institute Inc., Cary, North Carolina), as applicable. Calculations will be based on the actual sampling times recorded during the study.

- Time delay between the time of dosing and time of appearance of molybdenum concentration (T_{lag}) in plasma
- Maximum observed concentration (C_{max})
- Time to maximum concentration (t_{max})
- Trough (predose) concentration observed at the start of the dosing interval (C_{trough})
- Area under the plasma concentration versus time curve (AUC) from time 0 to the last quantifiable concentration (AUC_t)
- AUC over the dosing interval (AUC_{tau})
- Accumulation ratio (AR) calculated as:

For 15 mg/day:

- $C_{max,Day25}/C_{max,Day1}$
- $C_{trough,Day26}/C_{trough,Day2}$
- $AUC_{tau,Day25}/AUC_{tau,Day1}$

For 30 mg/day:

- $C_{max,Day39}/C_{max,Day29,adjusted}$
- $C_{trough,Day40}/C_{trough,Day30,adjusted}$
- $AUC_{tau,Day39}/AUC_{tau,Day29,adjusted}$

Note: total molybdenum and PUF molybdenum concentration-time profiles on Day 28 after the last 15 mg ALXN1840 dose will be extrapolated to Day 29 (0-24 hr) and subtracted from the observed Day 29 concentration-time profiles after the first 30 mg

ALXN1840 dose for the estimation of the $C_{\max, \text{Day}29, \text{adjusted}}$, $C_{\text{trough}, \text{Day}30, \text{adjusted}}$, and $AUC_{\tau, \text{Day}29, \text{adjusted}}$.

- Apparent terminal phase elimination rate constant (λ_z)
- Terminal elimination half-life ($t_{1/2}$)
- Apparent total body clearance (CL/F) of ALXN1840 from plasma
- Apparent volume of distribution (V_d/F).

Additional plasma PK parameters may be calculated if deemed appropriate.

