Blood sampling for pharmacokinetic (PK)/pharmacodynamic (PD) will occur over the 24-hour dosing period on Days 1, 25, 29, and 39. Pre-dose PK samples will be collected at all time points during the intake and output collection period to help characterize PK during accumulation (Days 1 through 9 for 15 mg and Days 31 through 35 for 30 mg) and at steady state (Days 25 through 28 for 15 mg and Days 36 through 39 for 30 mg).

This study incorporates the use of an adaptive design. Adaptive features may be implemented at the discretion of the Investigator to support conduct of the study. Such adaptive features do not require amendment of the protocol. Adaptive features and their limits are described in the [Protocol Table 4](#).

The overall objective of this Interim Statistical Analysis Plan (SAP) is to describe the second and subsequent analysis of interim data from Study ALXN1840-WD-204 to support the ALXN1840 regulatory submissions.

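### Do the 30 mg accumulation ratios and the Day 1 AUC to infinity need tighter extrapolation rules?

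*SAP*

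**What the plan says.** SAP 7.4.3 defines three accumulation ratios at 30 mg: Cmax and AUCtau on Day 39, and Ctrough on Day 40, each divided by an adjusted Day 29 or Day 30 value. The adjustment removes what is left of the 15 mg doses: the "concentration-time profiles on Day 28 after the last 15 mg ALXN1840 dose will be extrapolated to Day 29 (0-24 hr") and then subtracted. Protocol 9.4.4 has the same rule: the profile is "extrapolated to Day 29 (0-24 hr) and subtracted from the observed Day 29 concentration-time profiles after the first 30 mg" dose.

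Serial sampling "will occur over the 24-hour dosing period on Days 1, 25, 29, and 39". The protocol schema (1.2) lists "Pre-dose PK/PD sampling days: Days 4 - 7, Days 26 - 28, Days 30 - 38", and the Schedule of Activities (1.3) says of the routine samples that "Blood sampling for PK/PD will occur before ALXN1840 administration and represents a predose trough". In protocol Table 2 the serial days have a sample 0.5 h before dosing, then samples to 24 h, and "Hour 24 PK/PD sampling is to occur just prior to the next-day dose of ALXN1840".

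SAP 7.4.3 also lists "AUC from time 0 to infinity" for Day 1 only, with a dose-normalised version. The whole parameter list is limited to what the data allow. Analysis is noncompartmental, on individual actual sampling times, and lambda_z is one of the listed parameters. Protocol 2.2 supplies the kinetics: "Based on a total molybdenum PK half-life of approximately 24 - 51 hours", with a peak at about 4.54 h.

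**The concern.** Read literally, the rule extrapolates a profile that is not collected. After the Day 28 dose the only sample before the first 30 mg dose is the Day 29 pre-dose sample. Neither document names that sample as the starting point, says where the decline comes from, or gives acceptance criteria for lambda_z. The subtraction enters the denominator of all three 30 mg ratios, and the protocol itself reports two half-lives about a factor of two apart. Two analysts could therefore report different ratios from the same data.

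The Day 1 AUC to infinity raises a related worry. When more than half of an area is extrapolated from a 24 h profile, the figure depends heavily on a weakly estimated slope, and the SAP sets no point at which it would be flagged or withheld.

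At stake are secondary PK descriptors in about 10 participants, in an SAP written for interim analyses that support regulatory submissions.

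**Working it through.** The documents state no extrapolated share or expected ratio, so there is no plan figure to reproduce first.

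**Inputs.** Half-life 24 h (participants with Wilson disease, Days 84 and 168) and 51 h (60 mg single dose); peak at 4.54 h (protocol 2.2). 15 mg on Days 1-28, 30 mg on Days 29-39. Assumed: one compartment, first-order absorption, total molybdenum only (no half-life is given for ultrafiltrate molybdenum), no dietary background.

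**Rates.** k = ln 2 / half-life = 0.02888/h or 0.01359/h. Solving ln(ka/k)/(ka − k) = 4.54 gives ka = 0.745/h or 0.949/h.

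**Share of Day 1 AUC to infinity beyond 24 h.** f = [exp(−24k)/k − exp(−24ka)/ka] / (1/k − 1/ka); the second term in the numerator is negligible.
- 24 h: 0.500 × 34.62 / (34.62 − 1.34) = 17.31/33.28 = 52%.
- 51 h: 0.7217 × 73.58 / (73.58 − 1.05) = 53.10/72.52 = 73%.

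**Carry-over on Day 29**, with the AUC to infinity of one 15 mg dose as the unit. At steady state the 15 mg carry-over contributes f, and the new 30 mg dose contributes 2(1 − f).
- 24 h: 0.520 / (0.520 + 0.960) = 0.520/1.480 = 35%.
- 51 h: 0.732 / (0.732 + 0.536) = 0.732/1.268 = 58%.

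**AUC ratio with the right slope.** Superposing all doses gives a Day 39 AUC of 1.9995 (24 h) or 1.972 (51 h).
- 24 h: 1.9995 / (1.480 − 0.520) = 2.08.
- 51 h: 1.972 / (1.268 − 0.732) = 3.68.

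**AUC ratio with the other study's half-life imposed.** The Day 29 pre-dose value is decayed with the wrong slope.
- True 24 h, 51 h slope: carry-over becomes 0.615; 1.9995 / (1.480 − 0.615) = 2.31.
- True 51 h, 24 h slope: carry-over becomes 0.619; 1.972 / (1.268 − 0.619) = 3.04.

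In the same two cases the trough ratio goes from 2.00 to 2.57 and from 3.54 to 2.53; the Cmax ratio goes from 2.06 to 2.13 and from 3.61 to 3.23.

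**Ratios with the participant's own slope.** The Day 29 pre-dose value is decayed with lambda_z fitted to the model values at 8, 12 and 24 h on one sampled day:

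| Slope from | AUC ratio, 24 h | AUC ratio, 51 h | Trough ratio, 24 h | Trough ratio, 51 h |
|---|---|---|---|---|
| Day 1 | 2.085 | 3.683 | 2.003 | 3.546 |
| Day 25 | 2.085 | 3.682 | 2.001 | 3.544 |
| Day 29 | 2.085 | 3.682 | 2.002 | 3.544 |
| Day 39 | 2.085 | 3.682 | 2.001 | 3.544 |
| Truth | 2.084 | 3.681 | 2.000 | 3.543 |

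The choice of day moves the AUC ratio by about 0.001 and the trough ratio by about 0.002.

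**Starting point.** The Day 29 sample at −0.5 h falls 24 − 0.5 = 23.5 h after the Day 28 dose. It is a measured point on the very curve the rule extrapolates.

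**The case for a change.** The best case for a change is that the text does not forbid an outside half-life. The protocol's two values could also mean that kinetics change with repeated dosing. If they do, methods diverge: with a half-life moving from 51 h on Day 1 to 24 h later, superposing Day 1 and Day 25 profiles gives an AUC ratio of 1.91 against a true 2.08, and a trough ratio of 1.66 against 2.00. The worst wrong-slope case moves the trough ratio by (2.53 − 3.54)/3.54 = −28%. Writing down the anchor and the slope would cost only wording.

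The omission stands as a matter of text. But SAP 7.4.3 specifies individual noncompartmental analysis and lists lambda_z, so imposing another study's half-life would go against the method described. Day 25 lies in the designated 15 mg steady-state period and is the nearest serially sampled 15 mg day to Day 29, so it is the obvious source even if kinetics have shifted since Day 1.

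A fixed formula would also gain little accuracy. Post-peak sampling from 5 to 24 h covers only 19/24 = 0.79 or 19/51 = 0.37 of a half-life. With an assumed 5% random error per sample and a true half-life of 51 h, the Day 25 slope rule gives 90% ranges of 3.22 to 4.41 for the AUC ratio and 2.90 to 4.85 for the trough ratio. It would also decay any dietary molybdenum background towards zero, which matters most for ultrafiltrate molybdenum. If background were 10% to 20% of the pre-dose value (an assumption; the documents give none), the AUC ratio at 51 h would read 3.83 to 3.97 instead of 3.68.

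On AUC to infinity, the large extrapolated share is a fair point. However, dose proportionality uses dose-normalised Cmax and AUCt on Days 25 and 39, and nothing in either document says clearance will be based on AUC to infinity. Its absence from the protocol's list is covered by protocol 9.4.4, which allows additional PK parameters.

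**Conclusion.** The concern describes the text correctly, but it amounts to missing detail that a PK analyst would fill sensibly: start from the measured Day 29 pre-dose value, use the participant's own decline, and show the extrapolated percentage next to any Day 1 AUC to infinity. Done that way, the choice among sampled days changes the 30 mg AUC ratio by about 0.001 (2.08 to 2.09 at 24 h, 3.68 at 51 h). The shifts to 2.31 and 3.04 are worst cases that need an outside half-life.

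This rests on one-compartment kinetics that stay constant over the study, no assay error and no dietary background, and it covers total molybdenum only. Real data will scatter more, but that scatter comes from the 24 h sampling span and rewording would not remove it.

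No hypothesis is tested. The accumulation objective is assigned to molybdenum balance, and the accumulation ratios are only items in a PK parameter list. Copper balance, molybdenum balance, the 15 mg ratios and dose proportionality are unaffected. No change to the plan is called for.
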